4.8.2 Clinical studies with Novartis Vaccines HIV-1 subunit protein vaccines with MF59

Although Novartis Bivalent Subtype C gp120 proteins have not yet been administered to humans, other closely related recombinant monomeric (gp120) subunit vaccine formulations from Novartis Vaccines and Diagnostics (formerly Chiron) have been tested in many clinical trials. In addition, recombinant oligomeric (o-gp140) Env proteins for subtypes B and C from Novartis have been or are currently in clinical trials. Overall, in these studies, recombinant HIV-Env proteins manufactured by Novartis were well tolerated and immunogenic. In most cases, recombinant HIV-Env proteins (either gp120 or gp140) were CHO-based and administered with MF59, Novartis' proprietary oil-inwater emulsion adjuvant [64]. MF59 safety has been established in clinical studies as well as in commercial products. A seasonal influenza vaccine adjuvanted with MF59 (Fluad[®]) is licensed in the EU and other countries for use in the elderly. MF59 is also used in a pre-pandemic H5N1 influenza vaccine (Aflunov[®]) licensed in the EU for use in adults, and in 2 pandemic H1N1 influenza vaccines (Focetria[®] and Celtura[®]), licensed in the EU and other countries for use in the number of the set of the

Recombinant monomeric (gp120) vaccine candidates studied include Chiron's early gp120-based candidates from subtypes B and E, most of which were CHO-based and administered with MF59. More than 1200 subjects participated in the evaluation of the Chiron HIV SF2 gp120/MF59 vaccine and the Chiron HIV CM235 Thai E gp120/MF59 vaccine [62,65-69]. Two clinical trials were conducted using Novartis CHO-based subtype B gp140 recombinant Env protein with MF59. There are 3 ongoing phase 1 studies with Novartis CHO-based subtype C gp140/MF59, 2 of them are being conducted by the NIH-sponsored HVTN in the US and the RSA. Additionally, several HVTN phase

1/2a studies testing the protein/MF59 combination from HVTN 108 are scheduled to start as early as Q1 2015. Table 4-10 summarizes clinical trial experience with Novartis gp120 and gp140 recombinant vaccine candidates.

Candidate vaccine	# receiving Novartis protein	Protocol	Status
Yeast derived recombinant subtype B SF2 Env 2-3 protein with MF59 and MTP-PE	60	AVEG 005 A/B/C	Completed
SF-2 gp120 (CHO) with MF59 and MTP-PE	50	AVEG 007 A/B/C	Completed
SF2 gp120 (CHO)/MF59 and ALVAC	40	AVEG 012A 012B	Completed
SF2 gp120 (CHO) with MF59, SAF/2, SAF2 + MDP	107	AVEG 015	Completed
SF2 gp120 (CHO)/MF59 and ALVAC	47	AVEG 022A	Completed
SF2 gp120 (CHO) with MF59	24	AVEG 024	Completed
SF2 gp120 (CHO)/MF59 and ALVAC	85	AVEG 026	Completed
SF2 gp120 (CHO)/MF59 and ALVAC	22	AVEG 029	Completed
SF2 gp120 (CHO) +/- yeast derived p24/MF59 and ALVAC	56	AVEG 032	Completed
SF2 gp120 (CHO) with MF59	126	AVEG201	Completed
SF2 gp120 (CHO)/MF59 and ALVAC	140	AVEG 202	Completed
SF2 gp120 & CM235 gp120 (CHO)/MF59 and ALVAC	45	RV132	Completed
Subtype B (SF162) gp140 (CHO) /MF59 and Subtype B DNA/PLG	90	HVTN 049	Completed
Subtype B (SF162) gp140 (CHO) /MF59 IN with LTK63	20	C86P1	Completed
Subtype C (TV1) gp140 (CHO)/MF59 and SAAVI DNA-C2 and SAAVI MVA-C	24	HVTN073E	Completed
Subtype C (TV1) gp140 (CHO) & ISS TAT	11	ISS P-002	Terminated*
Subtype C (TV1) gp140 (CHO)/MF59	36	HVTN 088	Completed
Subtype C (TV1) gp140 (CHO)/MF59 and SAAVI DNA-C2 and SAAVI MVA-C	110	HVTN 086	Completed
Bivalent Subtype C gp120/MF59 and ALVAC-HIV (vCP2438)	210	HVTN 100	Planned

Table 4-10 Novartis recombinant gp120 and gp140 vaccines in human clinical trials* [67]

* Due to slow enrollment and expiration of the study product stability program.

In general, these recombinant protein vaccines were immunogenic and well tolerated with no unusual or serious vaccine-associated AEs reported. Most of the reactions were mild to moderate in nature, and of short duration [4,62,65-71].

4.8.2.1 Summary of safety, reactogenicity, and tolerability from recent human experience

There were 2 clinical trials conducted recently using Novartis CHO-based subtype B gp140 with MF59. In addition there have been 4 recent clinical trials using Novartis CHO-based subtype C gp140.

A phase 1 single-center trial (C86P1) was conducted using Novartis CHO-based subtype B gp140 recombinant Env protein in Great Britain by the Mucosal Vaccines for Poverty Related Diseases (MUVAPRED) Consortium to assess safety, tolerability, and immunogenicity of IN administration of subtype B gp140 with and without the mucosal adjuvant LTK63 (detoxified mutant heat labile protein) followed by IM boosting with subtype B gp140/MF59. This study enrolled 30 healthy volunteers aged 18-45, with 20 to

receive gp140. The protocol was amended to halt further IN administration of LTK63 following a report of an AE (ie, facial nerve paralysis) with a possible association with the LTK63 adjuvant in another study [72]. During the study, there was 1 SAE reported of Bell's Palsy (facial nerve paralysis) considered possibly related to the study vaccine LTK63 in a subject who never received any subtype B gp140 protein or any protein with MF59 adjuvant. IN vaccination was reactogenic resulting in upper respiratory tract symptoms including nasal congestion, nasal discomfort, pharyngo-laryngeal pain and rhinorrhea. The subtype B gp140 MF59 was well tolerated following IM boost.

Two other recent phase 1 studies with Novartis subtype C gp140/MF59 have been conducted by the HVTN in the US and the RSA. In addition, 1 phase 1 trial was conducted by the Istituto Superiore di Sanità (ISS) in Italy. One of these trials, HVTN 088, was conducted in the United States in order to evaluate the safety and immunogenicity of a long-interval, cross-clade subtype C gp140/MF59 boost in subjects previously administered subtype B gp120/MF59 or subtype B gp140/MF59 in previous trials. This included subjects from the HVTN049 DNA/PLG prime, gp140/MF59 boost study described above. The study enrolled 16 previously vaccinated subjects and 20 naive controls. Individuals were identified who had received a clade B Env protein with MF59 4-17 years earlier, most in combination with a DNA or ALVAC prime. These individuals were enrolled in HVTN088 to receive a clade C protein boost in an open label phase 1 trial. There have been 3 SAEs reported in this trial, 1 involving traumatic injury, 1 instance of gastroenteritis, and 1 of appendicitis. All of these were assessed as unrelated to study agents.

The second HVTN study, HVTN 086, was conducted in the RSA. It evaluated the safety and immunogenicity of various combinations of SAAVI DNA-C2, SAAVI MVA-C, and Novartis subtype C gp140/MF59. All scheduled clinic visits have been completed, though study participants remain subject to annual contacts to assess their health status. This study enrolled 184 subjects. To date, 6 SAEs have been reported in this study, 1 case of acute tonsillitis that required hospitalization, 1 of schizophrenia requiring hospitalization (later determined to be a pre-existing condition), 1 of pelvic inflammatory disease, 1 soft-tissue injury, 1 instance of anemia, and 1 instance of alcohol-related cardiomyopathy. All were assessed as not related to the study products.

The ISS study (ISS P-002) conducted in Italy examined the safety and immunogenicity of subtype C gp140 co-administered with ISS TAT compared to subtype C gp140 alone or TAT alone. The study includes intradermal and IM injections (100 mcg for subtype C gp140 and 7.5 mcg for ISS TAT). This study did not include MF59. This study was stopped early due to slow enrollment and subsequent expiration for the study product stability program. No SAEs were reported in this study.

4.8.2.2 Summary of immunogenicity from recent human experience

The immunogenicity of Novartis recombinant proteins has been demonstrated consistently in all clinical trials and in both of the recently completed studies using Novartis CHO-based subtype B gp140 MF59. In the HVTN 049 DNA/PLG prime protein boost study, the primary cellular immunogenicity endpoints included IFN-y ELISpot and ICS responses. Immunogenicity was assessed 14 days after each vaccination. Envspecific IFN-y ELISpot response rates did not increase substantially after the 3 1000-mcg DNA/PLG prime vaccinations (6/27) compared to baseline, but did rise after the first protein/MF59 boost (14/25). nAb titers against the homologous SF162 isolate were undetectable after the third 1000 mcg DNA/PLG priming vaccination. Neutralization was boosted to high titers in all subjects following the second protein boost. Similarly in the group of subjects who received subtype B gp140/MF59 without a DNA/PLG prime, a nearly complete response to the SF162 isolate was observed at the second vaccination (all but 1 subject) which lasted through the third vaccination. Binding Ab titers against Env. measured by enzyme-linked immunosorbent assay (ELISA), were detected following the first subtype B gp140/MF59 boost and were very high following the second boost administration [21].

The C86P2 MUVAPRED IN study, demonstrated immunogenicity with considerable IgG and IgA Ab responses to subtype B gp140 in serum, cervical, and vaginal secretions of subjects following IN administration of subtype B gp140 with the adjuvant LTK63 and an IM boost with subtype B gp140 and M59 adjuvant. nAb responses against the homologous SF162 were also detected in all groups following IM boost with subtype B gp140 and MF59 adjuvant.

Available data from HVTN 073E show that boosting with protein improves binding and neutralizing antibody responses for DNA/MVA primed subjects. All participants who received the protein boost had binding antibody responses to TV1.21 gp140 2 weeks after the last protein boost and these responses persisted in all participants 6 months later. After the last protein boost, neutralizing antibody responses to MW965.26 were seen in all participants and persisted in 75% of participants for at least 6 months. Notably, neutralizing antibody responses, which were not detected in the main HVTN 073/SAAVI 102 dataset, were detected after a single protein boost in the study extension. In the absence of priming, several protein administrations are typically required to elicit neutralizing antibody responses. That these responses were detected after a single dose

indicates efficient priming by the DNA/MVA regimen and points to protein boosts as an effective way to boost such responses.

In addition, in the subtype C gp140/MF59 HVTN 088 long-interval boost study 16 previously primed volunteers and 20 naïve volunteers each received 2 doses of the subtype C gp140/MF59 given 6 months apart. HIV-1-specific CD4+ and CD8+ T-cell responses were measured by an ICS assay. Ab responses were measured with a Luminex binding Ab assay and a nAb assay in TZM-bl cells. Despite the long interval (4-17 years from prior protein/MF59 administration), 5 of 16 (31%) of primed participants demonstrated CD4+ T-cell responses to Env at baseline, which increased to 12 of 16 (75%) after a single protein boost. IgG and IgA responses to Con S gp140were present in 64% (IgG) and 7% (IgA) of primed participants at baseline, and rose to 93% and 85%, respectively, after 1 dose of protein. 71% of primed participants demonstrated nAb against Tier 1 clade B isolate MN at baseline. After a single booster dose of protein, 100% of the primed participants neutralized MN and 93% showed neutralizing activity against a clade C isolate, MW965.26. Unprimed participants did not demonstrate CD4+ responses or Ab responses to Env until after the second dose, which elicited IgG and IgA responses to vaccine-matched oligomeric TV1 Env in 88% and 50%, respectively. nAb developed to MN in 38% and to MW965.26 in 88% of the unprimed participants.

Three of the 4 vaccine regimens in HVTN 086 contained Novartis subtype C gp140/MF59, either as a boost following pox-vector (MVA) primes, administered concurrently with a pox-vector (MVA) vaccine, or in a concurrent pox-vector/protein boost and second protein boost following DNA plasmid primes. Ab responses were measured with a Luminex binding Ab assay and a nAb assay in TZM-bl cells. All three vaccine regimens containing subtype C gp140/MF59 elicited high rates (82–100%) and magnitudes of IgG binding Ab against a range of gp120 and gp140 antigens. All vaccine regimens had evidence of nAb to (Tier 1) HIV strains MN.3, MW965.26, and SF162.LS, with the MVA- and DNA-primed regimens showing the highest titers to MW965.26, a clade C strain. HIV-1 specific CD4+ and CD8+ T-cell responses to global potential T-cell epitopes (PTEg) were measured by an ICS assay. The MVA- and DNA-primed vaccine regimens elicited the highest rates of CD4+ T cells producing IFN- γ and/or IL-2 (77% and 45%, respectively), while the regimen with concurrent MVA/protein administration elicited the lowest rate (13%).

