HVTN 108 is one of the phase 1/2a studies planned within this program. Evaluation of DNA/protein and protein only regimens will provide an opportunity to compare the immunogenicity of these simpler, non-vector vaccine regimens. This study has 7 active arms and 1 placebo arm and will compare DNA priming administered at Months 0 and 1, followed by DNA + Protein + MF59 or AS01_B boosting at Months 3 and 6, versus DNA + Protein + MF59 or AS01_B co-administered at Months 0, 1, and 6. In addition, this study will evaluate Protein + AS01_B administered at Months 0, 1, and 6. Furthermore, to assess whether too high a protein dose in the presence of AS01_B adjuvant may overstimulate the immune system and thereby suppress responses, 2 different doses of each of the bivalent Env proteins will be evaluated: 20 mcg versus 100 mcg for each of the DNA containing regimens (see section 4.5.4).

How to identify the regimens which will be further assessed in a future efficacy trial will depend on the 'adequate take/potency' (ATP) as defined in Section 6.1.2. Meeting the ATP criteria is a necessity to move forward to efficacy testing, however in itself does not suffice for a regimen to qualify for further evaluation. Because many or all of the regimens of this study could hypothetically meet the ATP, further down-selection will be performed using secondary and exploratory objectives as described in Sections 5.2 and 5.3. In this way, those individual regimens which are able to elicit an immune response with a unique profile, and therefore warrant further evaluation, can be moved forward into a future efficacy trial. Such an efficacy trial could potentially include 1 or more of the vaccine regimens evaluated in this study, together with regimens from other phase 1/2a studies.

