magnitudes for any potential T-cell epitopes are greater in the DNA primed compared to NYVAC primed groups, with or without protein co-administration during the prime.

Co-administration of protein with DNA or NYVAC from the first injection leads to early (after 2nd immunization) induction of both binding and neutralizing antibody responses in group 2 and 4. Of note there is a trend to more durable antibody responses at the month 12 timepoint in group 4 (DNA / protein prime with NYVAC / protein boost). Additionally, co-administration of protein with DNA or NYVAC from priming substantially reduces the generation of IgA binding Ab responses to gp140 and gp120.

HVTN 092 (BB-IND 15315): DNA-HIV-PT123 in combination with bivalent NYVAC (NYVAC-HIV-PT1 and NYVAC-HIV-PT4) vaccines will provide additional safety and possibly immunogenicity data. The study opened in April, 2013 and is being conducted in the US and Lausanne, Switzerland. As of November 2013, 143 participants had been enrolled. The DNA-HIV-PT123 vaccine has been well-tolerated. The most common complaints have been mild or moderate injection site pain/tenderness, myalgia, headache, and malaise/fatigue. There have been no SAEs related to the DNA-HIV-PT123 vaccine. There was 1 SAE, a case of myocarditis, deemed related to NYVAC vaccination that prompted a hold on vaccinations.

HVTN 105 (BB-IND 15997): assesses several vaccine regimens of DNA-HIV-PT123 in combination with AIDSVAX B/E. The study opened in July, 2014 and is being conducted at multiple sites in the US. The study is fully enrolled and as of April 6, 2015, no SAEs have been reported. No AEs graded severe or higher have been reported, and all AEs deemed related to the study product have been assessed as mild. The DNA-HIV-PT123 vaccine has been well-tolerated. The most common complaints have been mild or moderate injection site pain/tenderness, headache, and malaise/fatigue.

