5.3 Exploratory objectives

Exploratory objective 1

• To evaluate the durability of immunogenicity of each vaccine regimen measured at Month 12 (6 months after the 4th vaccination)

Exploratory objective 2

• To further evaluate immunogenicity of each vaccine regimen, additional immunogenicity assays may be performed on blood and mucosal samples, including samples from other timepoints, based on the HVTN Laboratory Assay Algorithm

Exploratory objective 3

• To assess whether the diversity of gut microbiome correlates with vaccine responses using optionally provided stool specimens.

Exploratory objective 4

• To conduct analyses related to furthering the understanding of HIV, immunology, vaccines, and clinical trial conduct

6 Statistical considerations

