6.4.4 Immunogenicity analysis

6.4.4.1 General approach

For the statistical analysis of immunogenicity endpoints, data from enrolled participants will be used according to the initial randomization assignment regardless of how many injections they received. Additional analyses may be performed, limited to participants who received all scheduled injections per protocol. Assay results that are unreliable, from specimens collected outside of the visit window, or from HIV-infected participants postinfection are excluded. Since the exact date of HIV infection is unknown, any assay data from blood draws 4 weeks prior to an infected participant's last seronegative sample and thereafter may be excluded. If an HIV-infected participant does not have a seronegative sample postenrollment, then all data from that participant may be excluded from the analysis.

For each of the 11 primary endpoints listed in Table 6-3, response rates will be analyzed by tabulating the frequency of positive response for each endpoint and treatment group at each timepoint for which an assessment is performed. For CD4+ and CD8+ T-cell response, response rates to the individual peptide pools will also be calculated. Crude response rates will be presented with their corresponding 95% confidence interval estimate calculated using the score test method [73]. For secondary and exploratory assay endpoints, response rates and 95% confidence intervals will be calculated if appropriate for the endpoint. Criteria for a positive response for an assay will be described in the SAP.

All of the primary assays, and likely some of the secondary assays, will have quantitative assay data, including IgG binding antibody magnitude, neutralizing antibody titers, area under the magnitude-breadth curve [AUC-MB] for the neutralizing antibody assay, and percentage of positive cells from the ICS assay. Quantitative data will be displayed as graphical and tabular summaries of the distributions by antigen, treatment group, and timepoint. For all primary and secondary immunogenicity endpoints, box plots and plots of estimated reverse cumulative distribution curves will be presented by group.

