Based upon previous HVTN trials, missing 15% of immunogenicity results for a specific assay is common due to study participants terminating from the study early, problems in shipping specimens, or low cell viability of processed PBMCs. To achieve unbiased statistical estimation and inferences with standard methods applied in a complete-case manner (only including participants with observed data in the analysis), missing data need to be missing completely at random (MCAR). Following the most commonly used definition, MCAR assumes that the probability of an observation being missing does not depend on any participant characteristics (observed or unobserved). When missing data are minimal (specifically, if no more than 20% of participants are missing any values), then standard complete-case methods will be used, because violations of the MCAR assumption will have little impact on the estimates.

If a substantial amount of immunogenicity data are missing (at least 1 value missing from more than 20% of participants), then using the methods that require the MCAR assumption may give misleading results. In this situation, analyses of the immunogenicity endpoints at a specific timepoint will be performed using parametric generalized linear models fit by maximum likelihood. These methods provide unbiased estimation and inferences under the parametric modeling assumptions and the assumption that the missing data are missing at random (MAR). MAR assumes that the probability of an observation being missing may depend upon the observed responses and upon observed covariates, but not upon any unobserved factors. Generalized linear models for response rates will use a binomial error distribution and for quantitative endpoints, a normal error distribution. For assessing repeated immunogenicity measurement, linear mixed effects models will be used. If the immunological outcomes are left- and/or right- censored, then the linear mixed effects models of Hughes [75] will be used, because they accommodate the censoring. In addition, secondary analyses of repeated immunogenicity measurements may be done using weighted GEE [76] methods, which are valid under MAR. All of the models described above will include as covariates all available baseline predictors of the missing outcomes.

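### The durability objective is analysed one timepoint at a time, so a Month 12 level comparison cannot tell slower waning from a higher Month 6.5 peak; a within-person fold-decline could be added cheaply

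*Combined protocol and SAP*

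**What the plan says.** Section 5.3 states exploratory objective 1 as "To evaluate the durability of immunogenicity of each vaccine regimen measured at Month 12 (6 months after the 4th vaccination"). It gives no decline, fold-change or half-life measure. The background in section 4.8.2.2 likewise reports persistence in HVTN 073E as the share of participants still responding: all who got the protein boost had binding responses "2 weeks after the last protein boost and these responses persisted in all participants 6 months later".

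Section 6.4.4.1 sets out the analysis:

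- For the 11 primary endpoints, "response rates will be analyzed by tabulating the frequency of positive response for each endpoint and treatment group at each timepoint" at which an assay is run.
- For magnitudes, "Quantitative data will be displayed as graphical and tabular summaries of the distributions by antigen, treatment group, and timepoint".
- Two arms are compared with Fisher's test when one response rate is low (for example 20% or less). When both rates are high (for example 75% or more), a rank-sum or t-test on the continuous readout is used. A two-part test is available for mixtures. Each of these compares rates or levels, not change.
- If no more than 20% of participants have a missing value, complete-case methods apply. If more than 20% do, likelihood models apply, and it is in that paragraph that the section says "For assessing repeated immunogenicity measurement, linear mixed effects models will be used", with a censored-data version and an optional weighted GEE.

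On use of the results, section 4.3 says that, because many regimens may meet the adequate take/potency (ATP) condition, "further down-selection will be performed using secondary and exploratory objectives as described in Sections 5.2 and 5.3". Section 4.1, however, bases advancement on data collected through Month 6.5. Section 10.3 and a footnote to Appendix G make assays at timepoints such as Month 12 conditional on the responders seen.

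**The concern.** The level at Month 12 is the level at Month 6.5 less the decline between them. Two arms can differ at Month 12 because one peaked higher, because one waned more slowly, or both. A comparison of Month 12 levels sees only the sum.

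Peaks could well differ. Table 3-1 gives Groups 1-3 two protein doses and Groups 4-7 three, and the arms also differ in adjuvant and protein dose. An arm could be credited with durability when it only peaked higher. A real difference in waning could also be hidden when the faster-waning arm started higher.

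The model that could separate the two is named only in the high-missingness branch, so whether waning is modelled depends on the pattern of missing samples and not on the question asked. Even in that branch the contrast of interest is not stated.

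**Working it through.** **The plan's own sizing.** The plan gives no figure for durability. Its immunogenicity sizing uses n = 43 (50 enrolled less 7 missing; 50 × 0.85 = 42.5). At that n, all ten rows of Table 6-4 reproduce with the score interval. A simulation of the ATP rule at δ = 24% gives minimum power of 0.80, against the stated minimum of 80%. I therefore take 43 per arm as the working size.

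**Inputs the documents do not give (assumed).** Log10 SD 0.5 at each visit (range 0.4 to 0.6), within-person correlation r between visits of 0.5 to 0.8, 43 participants per arm with both samples, two-sided 5%.

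**Formulas (normal approximation).**
- SE of a difference in Month 12 means = SD × √(2/43).
- SD of the within-person change = SD × √(2(1 − r)).
- Power ≈ Φ(difference/SE − 1.96).

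**Scenario 1: identical decay, peaks 2-fold apart (0.3 log10).** SE = 0.5 × √(2/43) = 0.108, so 0.3/0.108 = 2.78 and Φ(2.78 − 1.96) = 0.79. At SD 0.4 and 0.6 the result is 0.94 and 0.64. Simulating the rank-sum test (4,000 trials) gives about 77% for the Month 12 comparison. The within-person change rejects in about 5%, its nominal rate. With 38 per arm the Month 12 figure is 70-72%.

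**Scenario 2: one arm peaks 0.25 log10 higher and declines 0.25 log10 more.** Month 12 levels are then equal, so the Month 12 test rejects in about 5% and misses the difference in waning in about 95%. For the within-person change:

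| r | SD of change | 0.25/SE | Power, normal | Power, rank-sum simulation |
|---|---|---|---|---|
| 0.5 | 0.50 | 2.32 | 0.64 | about 61% |
| 0.7 | 0.39 | 2.99 | 0.85 | about 82% |
| 0.8 | 0.32 | 3.67 | 0.96 | about 94% |

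**Scenario 3: equal peaks, decline differs by 0.25 log10.** The Month 12 test has about 60% power. The within-person change has about 60%, 82% and 94% at r = 0.5, 0.7 and 0.8. At r = 0.5 or below there is no gain in power; what remains is freedom from the peak.

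**Would the 20% trigger be met?** Section 6.1 expects 15% missing at Month 6.5. Month 12 missingness is not stated; assume 15% as well. Participants missing at least one of the two values are then:
- 15% if the same people miss both;
- 1 − 0.85² = 27.8% if misses are independent;
- 30% if the misses do not overlap.

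The chance that more than 20% of 334 have a missing value is 0.008 in the first case and above 0.999 in the second. With 20% missing at Month 12 and full overlap it is 0.51.

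**The case against.** Several points on the other side stand.

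- **Month 12 level is a legitimate durability measure.** Residual level may be what matters, and section 5.3 defines durability at that visit. An arm that falls steeply from a high peak yet stays higher at Month 12 should not be called less durable on the decline alone. This is why the decline should be added, not substituted.
- **The trigger is not remote.** Once two visits are counted it may well be met, and the mixed-model sentence could be read as unconditional. Its place in the high-missingness paragraph makes the conditional reading the natural one, and neither reading supplies the contrast.
- **Per-timepoint summaries let a reader see both visits.** They do, but without an interval or a comparison for the decline.
- **The expected formal comparisons are of adjuvant and of AS01B dose.** Within a schedule, those pairs receive the same number of protein doses, so dose count alone does not make their peaks differ. Adjuvant and protein dose still may.
- **The separate SAP, which is not included here, could already specify this.**

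Three stronger readings are tempting and are not supported:

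1. A reader might infer from the 100% persistence in HVTN 073E that binding response rates will sit at ceiling and the comparison will have almost no power. Section 6.4.4.1 moves to continuous readouts when both rates are high, so Fisher's test would not be used there. Those data also concern gp140 after DNA/MVA priming.
2. A reader might infer that the wrong regimen will advance. Section 4.3 points to the exploratory objectives, but section 4.1 bases advancement on data through Month 6.5. The two passages are in tension.
3. A reader might take the HVTN 096 remark in section 4.8.1 ("Of note there is a trend to more durable antibody responses at the month 12 timepoint in group 4") as evidence that these regimens differ in durability. That group was boosted with NYVAC and AIDSVAX B/E, which no arm here receives.

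**Conclusion.** The point holds in a limited form. The documents analyse durability by separate-timepoint rates and levels and name no Month 6.5 to Month 12 contrast, so a difference at Month 12 cannot be attributed to waning. Under the assumed SD and 43 per arm, the Month 12 test flags a pure 2-fold peak difference in about 77% of trials (64% to 94% by normal approximation over SD 0.6 to 0.4) and misses an offsetting difference in decay in about 95%. These figures show the mechanism. They do not predict this trial, because the documents give neither the SD, nor the correlation, nor the expected peak differences.

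The severity is minor and the change optional. The objective is exploratory, Month 12 assays are conditional, the link to down-selection is uncertain, and the primary ATP assessment is unaffected.

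**What to change.** In section 6.4.4.1 and the SAP:

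1. Keep the Month 12 response rates and levels as a durability measure.
2. For the quantitative binding (gp120, V1V2) and neutralizing endpoints assayed at both visits, add the within-participant change in log10 magnitude from Month 6.5 to Month 12.
3. Estimate it with the linear mixed model already named (arm, visit, arm-by-visit, and region as the stratification factor), using the censored version where values lie at assay limits, whatever the amount of missing data.
4. Report each arm's geometric mean fold-decline with a 95% CI, and the arm-by-visit contrasts, labelled exploratory and shown beside the Month 12 levels.
5. Fix this wording before the unblinded Month 6.5 analysis that section 6.4.5.2 allows.

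The cost is a few lines of text and one model. Appendix G already schedules the blood draws at days 182 and 364.

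The limits should be stated. The estimate rests mainly on participants assayed at both visits. Saturation of the assay at peak would understate the decline. A shift between assay runs would bias each arm's fold-decline, though it largely cancels between arms. A steep fall from a high peak must be read with the Month 12 level.
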